### AsBR

AsBR will be derived by inhibitor status and overall as follows:

$$(\text{number of bleeding events}) / (\text{observed treatment period of interest days}) * 365.25.$$

Only bleeding events requiring treatment will be included in the derivation of bleeding rates. The AsBR will be estimated for subjects who complete at least 8 weeks of treatment on the given inhibitor status using the subject's observed data. If the subject does not complete at least 8 weeks of treatment on the given inhibitor status, then the AsBR will be considered missing.

The number of spontaneous bleeding episodes per year based on a Poisson model and associated 95% CI and the number and percentage of subjects with zero bleeding episodes will be presented. In addition, the rate ratio of Prophylaxis modality to On-Demand modality (Prophylaxis- On-Demand) will be presented, along with the associated 95% CI, as obtained by the Poisson model.

Spontaneous bleeding episodes are those classified as 'Non-traumatic' in e-Diary or 'Spontaneous' in the eCRF. Annualized spontaneous bleeding rate will also be summarized for the following subgroup:

- Positive non-inhibitory Anti-Drug Antibodies (ADAs) and negative during the study
- Age based on age in this study: for PTPs: 0 to < 6 years,  $\geq 6$  to < 12 years,  $\geq 12$  to < 18 years and  $\geq 18$  to  $\leq 65$  years, 0 to <12 years,  $\geq 12$  to  $\leq 65$  years.
- Prophylaxis frequency: every second day, 3 times per week, 2 times per week, other regimen.

In these subgroup analyses rate ratio of Prophylaxis modality to On-Demand modality won't be displayed.

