2.1.2 Primary Endpoints

In **Arms 1 and 3 (PTPs)**, the primary endpoint is the incidence of inhibitor formation to FVIII in at least 200 PTPs with at least 100 EDs of rVIII-SingleChain.

In **Arm 2 (PUPs)**, the primary endpoints are:

- Incidence of high-titer inhibitor formation to FVIII (ie, inhibitor titer of ≥ 5 Bethesda units [BU]/mL) in PUPs with at least 50 EDs of rVIII-SingleChain.
- Treatment success for **major** bleeding episodes, defined as a rating of "excellent" or "good" on the investigator's clinical assessment of hemostatic efficacy 4-point scale.
- Annualized spontaneous bleeding rate (AsBR) during prophylaxis and on-demand treatment.

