11.3.2.1 Primary Efficacy Analysis

For **Arms 1 and 3 (PTPs)**, there is no primary efficacy endpoint.

For **Arm 2 (PUPs)**, the analyses of the primary efficacy endpoints are outlined below:

- The investigator's clinical assessment of hemostatic efficacy for the treatment of **major** bleeding episodes, based on the 4-point ordinal scale (excellent, good, moderate, poor / no response), will be tabulated. The percentage of major bleeding episodes treated successfully (defined as ratings of excellent or good) will be summarized, and reported together with a two-sided 95% CI. To estimate the proportion, the denominator will include all treated bleeding episodes categorized as major. To account for within-subject correlation, generalized linear modeling using SAS' GENMOD procedure will be utilized. The model will contain only the intercept term. The binomial distribution with logit link function will be specified.
- The AsBR will be derived for each subject as follows: ((number of spontaneous bleeding episodes) / (observed treatment period of interest))*365.25. The AsBR will be summarized by regimen (on-demand or prophylaxis) using descriptive statistics. In addition, the number of spontaneous bleeding episodes per year and associated 95% CI will be estimated based on a Poisson model. Generalized linear modeling using SAS' GENMOD procedure will be utilized. The Poisson distribution with log link function, and log_time offset will be specified. The Poisson-based number of spontaneous bleeding episodes per year will be presented by regimen (on-demand or prophylaxis).

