## 4.6 Efficacy Analysis

The efficacy endpoints will be summarized and analyzed for the Efficacy population unless otherwise specified. The surgery substudy efficacy data will be summarized for the Surgery population. Efficacy analyses will be performed separately for the PTPs and PUPs and by modality. Efficacy results for the PUPs will be presented by inhibitor status (positive, negative) and overall.

The efficacy evaluation period begins on Treatment Day 1 date in this study and ends at the End of study Visit in this study or the last date of dose, whichever occurs later. Only those treated bleeding episodes and doses which fall within the efficacy evaluation period will count

towards the efficacy evaluation. The summary statistics to be presented are described in [Section 4.1](#).

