## **4.6.2 Secondary Efficacy Endpoints**

### **4.6.2.1 Annualized Bleeding Rate**

Annualized bleeding rate, as defined in [Section 4.6.1](#), will be derived also by type of bleed, i.e., for total, spontaneous, traumatic, unknown and joint bleeds for PTPs. Only treated bleeds will be considered. The ABR will be estimated for subjects who complete at least 8 weeks of treatment on the given regimen using the subject's observed data. If the subject does not complete at least 8 weeks of treatment on the given regimen, or has no treated bleeding events while on the given regimen, then the ABR will be considered missing.

A summary of ABR will be performed by inhibitor status if the efficacy evaluation period is greater or equal than 8 weeks on the given inhibitor status.

For PUPs, as secondary efficacy endpoints, annualized bleeding rate, as defined in [Section 4.6.1](#), will be presented also for traumatic, unknown and joint bleeds.

Annualized Bleeding Rates will be derived also separately for the **CCI** Population.

A specific analysis will be produced for annualized bleeding rates while subjects are inhibitor positive on PUPs.

Bleeding events details will be listed while subjects are inhibitor positive and for all subjects.

Subjects < 8 weeks of efficacy assessment will be listed.

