#### **4.6.2.2 Number of infusions of CSL627 required to achieve hemostasis (1, 2, 3, or >3)**

[figure not shown]
The number of bleeding episodes and the number of treated bleeds, the number and the percentages of subjects with  $\geq 1$  bleeding episodes and with  $\geq 1$  treated bleeding episodes will be presented.

The number and percentage of bleeding episodes requiring 1, 2, 3 or more than 3 infusions of CSL627 to achieve hemostasis will be summarized using frequency counts and percentages. No statistical inference will be performed on this data.

In addition, the following parameters will be presented:

- Total dose per bleeding episode in IU and IU/Kg:
  - calculated as: sum of doses (IU) per bleeding episode;
  - calculated as: sum of doses (IU/Kg) per bleeding episode;
- Total dose per injection per bleeding episode in IU and IU/Kg:
  - i.e. total dose (IU) per injection given for any bleeding episodes;
  - i.e. total dose (IU/Kg) per injection given for any bleeding episode.

Treatment Success to achieve hemostasis will be as illustrated:

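### The primary AsBR counts all spontaneous bleeds in the protocol but only bleeds requiring treatment in the SAP, and SAP 4.11 does not declare the difference

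*SAP*

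**What the plan says.** Protocol 2.1.2 names the Arm 2 primary endpoint as "Annualized spontaneous bleeding rate (AsBR) during prophylaxis and on-demand treatment", with no treatment condition. Protocol 11.3.2.1 gives the per-subject formula, "number of spontaneous bleeding episodes) / (observed treatment period of interest))*365.25", also without one.

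For the other primary efficacy endpoint, the same protocol section does state the condition: "the denominator will include all treated bleeding episodes categorized as major". Protocol 11.3.2.2 then presents all bleeding episodes and treated bleeding episodes as two separate counts.

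The SAP restricts the numerator in three places:
- SAP 4.6, for efficacy generally: "Only those treated bleeding episodes and doses which fall within the efficacy evaluation period will count" towards the evaluation.
- SAP 4.6.1.1, for the primary AsBR: "Only bleeding events requiring treatment will be included in the derivation of bleeding rates".
- SAP 4.6.2.1, for the secondary annualized bleeding rate: "Only treated bleeds will be considered".

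SAP 4.6.2.2 nevertheless presents "The number of bleeding episodes and the number of treated bleeds" as separate figures, and SAP 4.6.1.1 lists PUP bleeds that were not treated with study product.

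For Sections 4.6.1 and 4.6.2.1, SAP 4.11 records one change from the protocol, the 8-week minimum evaluation period. It does not record the restriction to treated bleeds.

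**The concern.** The two documents define a primary endpoint differently. Someone who reads the protocol and then the study report would take the reported AsBR to cover all spontaneous bleeds. The protocol's wording does not look careless, because it says treated where it means treated, in the same section and in the next.

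The sponsor judged the 8-week rule to be a change worth declaring for this analysis. A narrower numerator is at least as substantive. No all-bleed AsBR is planned as a sensitivity analysis, whereas the major-bleed success endpoint has two sensitivity analyses.

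The restriction is also not fully specified. A bleed requiring treatment and a treated bleed are not the same thing, and the SAP uses both expressions. It does not say whether a bleed treated with another product enters the AsBR. That could matter for the planned AsBR by inhibitor status: Protocol 5.5 permits bypassing agents in subjects with inhibitors, and the efficacy population in SAP 3.5.3 includes those subjects.

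**Working it through.** Neither document states an AsBR value, a target or a power calculation, so there is no figure of the plan's own to reproduce. The check is algebraic.

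**Inputs from the documents.** The numerator is all spontaneous bleeds (Protocol 11.3.2.1) or only those requiring treatment (SAP 4.6.1.1). Both annualize with 365.25 over the observed period. The Poisson model uses a log link with log time as offset.

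**Assumed input.** *u* is the share of spontaneous bleeds left untreated. The documents do not give it.

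**Direction.** Treated bleeds are a subset of all bleeds, and the 8-week rule depends on time rather than on bleeds. The same subjects and the same time T therefore enter both rates:

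AsBR(all) = (all spontaneous bleeds / T) × 365.25

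AsBR(treated) = (treated spontaneous bleeds / T) × 365.25 = (1 − u) × AsBR(all)

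Hence AsBR(treated) ≤ AsBR(all), with equality at u = 0. This holds for each subject with his own *u*. It also holds for the Poisson estimate by regimen, which is total bleeds divided by total time. It requires that a subject with no treated bleed keeps a rate of zero, as SAP 4.6.1.1 implies by reporting subjects with zero bleeds. SAP 4.6.2.1 sets such subjects to missing for the secondary rate, but that rule is not written for the primary AsBR.

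**Size, on assumed values.** The zero-bleed column assumes a Poisson mean of 2 spontaneous bleeds per subject over follow-up and uses exp(−2(1 − u)).

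| u (assumed) | 2.0/year becomes | 5.0/year becomes | Subjects with zero bleeds |
|---|---|---|---|
| 0 | 2.0 | 5.0 | 13.5% |
| 0.1 | 1.8 | 4.5 | 16.5% |
| 0.2 | 1.6 | 4.0 | 20.2% |
| 0.3 | 1.4 | 3.5 | 24.7% |

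**Rate ratio.** The prophylaxis/on-demand ratio in SAP 4.6.1.1 is multiplied by (1 − u for prophylaxis) / (1 − u for on-demand):
- equal shares of 0.1 and 0.1: 0.9 / 0.9 = 1.00, no change
- 0.3 on prophylaxis and 0.1 on-demand: 0.7 / 0.9 = 0.78
- 0.1 on prophylaxis and 0.3 on-demand: 0.9 / 0.7 = 1.29

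**Declaration.** SAP 4.11 covers Sections 4.6.1 and 4.6.2.1 with the 8-week rule only. The SAP's list of substantial changes does not mention the restriction either.

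**The case against.** The strongest reply is that the two sets of bleeds are meant to be nearly the same. Protocol 3.2.2 and 6.2.1 tell all subjects to treat bleeds with study product whichever regimen they are on, and SAP 3.2.3 repeats this. If they comply, *u* is close to zero. That stands, and it limits the likely size.

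Second, recording is organised around treatment. The home diary items in Protocol 8.3.1 are introduced as information on treatment received, and the eCRF items in Protocol 8.3.2 are recorded after a bleed is treated. Untreated bleeds may be under-recorded, which makes an all-bleed rate debatable as the sole main result. That also stands. It argues for showing both rates, not for omitting one.

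Third, Protocol 11.3 leaves the complete description of methods to the SAP, and the SAP states the restriction openly. A reader might infer a late or concealed change. The documents do not support that: the change list shows no such addition in Version 2 or 3, which suggests, without proving it, that the restriction was there from Version 1. Only the SAP 4.11 entry is missing.

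Fourth, much of any gap will be visible through the bleed counts and listings. This stands in part, since none of them is an annualized rate.

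Finally, separate counts of all and treated bleeds do not prove that untreated bleeds are expected. If treated there means treated with study product, the difference could include bleeds treated with something else. That uncertainty is itself a reason to define the term.

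**Conclusion.** The discrepancy is real and undeclared: as planned, the SAP does not produce the primary AsBR that the protocol defines. The SAP rate is lower than or equal to the protocol rate by the untreated share, given the same subjects and person-time and zero rates kept as zeros.

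The size is unknown and may be nil. The values of *u* and the rates of 2.0 and 5.0 per year are illustrations and do not come from the documents.

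A reader might infer that the restriction flatters prophylaxis, because the decision to treat a bleed could differ by regimen. The documents give no untreated share for either regimen, and the rate ratio can move in either direction. Nor does it necessarily improve the result: if every bleed is treated, nothing changes.

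The practical weight is low. Protocol 11.3 plans no p values, Protocol 11.1 has no sample size calculation, and AsBR has no success threshold for a shift to cross. It is a matter of consistency and transparency in a primary endpoint, and it is cheap to settle.

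**What to change.** - In SAP 4.6.1.1, report AsBR, its Poisson estimate with confidence interval and the zero-bleed percentage twice: for all recorded spontaneous bleeds, as in the protocol, and for treated spontaneous bleeds.
- Use one term throughout SAP 4.6, either treated or requiring treatment, and state whether a bleed treated with another product counts.
- List the restriction and its reason in SAP 4.11, next to the 8-week rule.

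The cost is one extra row per AsBR table and a sentence in SAP 4.11, using bleeds the SAP already plans to count or list. The downsides are a possibly slightly higher rate in the all-bleed row, and a footnote saying that untreated bleeds may be incompletely captured because diary and eCRF recording is framed around treatment. If the two rows agree, the question is closed.

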3.2.5 Change in Treatment Regimens and Dose Modifications

In all study arms, changes in treatment regimens (on-demand or prophylaxis) and dose modifications are allowed and will be permitted at the investigator's discretion. The timing of dose adjustment should be flexible and based on the type of bleeding episode, the location of the bleeding episode, the age of the patient, and bleeding phenotype. The eCRF should be updated accordingly for each change in treatment regimen. Compliance with the assigned dose regimen will be assessed using the criteria detailed in [Section 6.2.4](#).

Special considerations for Arm 2 (PUPs):

- Arm 2 PUPs **switching from on-demand to prophylaxis** during the treatment period should have monthly visits until 25 EDs, followed by visits every 3 months until End of Study.
- Arm 2 PUPs **switching from prophylaxis to on-demand** during the treatment period will have follow-up visits 1 month after each rVIII-SingleChain dose (see [Section 8.10.2](#) for details).

3.2.6

CCI

CCI

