11.3.2.2 Secondary Efficacy Analyses

- In **all study arms**, the analyses of the secondary efficacy endpoints are as follows: The primary efficacy analyses outlined in [Section 11.3.2.1](#) for the AsBR will be repeated for the ABR (traumatic, non-traumatic, and unknown).
- The number of bleeding episodes and the number of treated bleeding episodes will be presented. The number and percentage of bleeding episodes requiring 1, 2, 3, or > 3 injections of rVIII-SingleChain to achieve hemostasis will be tabulated. The total dose per bleeding episode (IU/kg) will be summarized using descriptive statistics.
- The consumption of rVIII-SingleChain, will be derived and expressed in terms of IU/kg per month, IU/kg per year, total IU per injection, per month and per year. Consumption will be summarized using descriptive statistics for on-demand, prophylaxis, and surgery.
- The investigator's clinical assessment of hemostatic efficacy for surgery based on the 4-point ordinal scale will be tabulated.

In **Arms 1 and 3 (PTPs)**, the following analysis will be performed in addition to those above:

- The investigator's clinical assessment of hemostatic efficacy for the treatment of bleeding episodes, based on the 4-point ordinal scale (excellent, good, moderate, poor / no response), will be tabulated by severity (major and non-major). The percentage of bleeding episodes treated successfully, defined as excellent or good) will be summarized and reported together with a two-sided 95% CI. In order to account for within-subject correlation, generalized linear modeling using SAS' GENMOD procedure will be utilized. The model will contain only the intercept term. The binomial distribution with logit link function will be specified.

In **Arm 2 (PUPs)**, the following analysis will be performed in addition to those above:

The investigator's clinical assessment of hemostatic efficacy for the treatment of **non-major** bleeding episodes will be analyzed as described in [Section 11.3.2.1](#) for major bleeding episodes

Details on the analyses for the secondary efficacy endpoints will be provided in the Statistical Analysis Plan (SAP).

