The above schema depicts a subject starting out as a negative inhibitor (-), which is the case for all subjects in the study. At some point in the study, i.e. at Time (c), his titre level went up and met the criteria for inhibitor positive status (+), which consisted of an initial titre value of  $\geq 0.6$  BU/mL, represented by (+) at Time (c), and was followed by a confirmatory titre value of  $\geq 0.6$  BU/mL in the next assessment, represented by (+)\* at Time (d). At Time (c), he is considered (+). When a subject becomes (+), the Investigator may administer an intensified prophylaxis (IP) treatment. Furthermore, he will be included in the CCI [REDACTED] to treat his inhibitory response to rVIII-SingleChain treatment. If the subject responds positively to IP and/or CCI [REDACTED], his titre values will improve (i.e. decrease) at later assessments. In the above schema, the subject became (-) at Time (e), which was followed by a confirmatory assessment (-)\* at Time (f) one month later. At Time (f), the subject is considered inhibitor eradicated.

From the above schema, we can state that:

Period of (+): Time reference after Time (c) up to Time (f), or Time (c) < Time reference  $\leq$  Time (f).

Period of (-): There will be two: on or before (+), and after (-)\*.

- On or before (+): Time (start) < Time reference  $\leq$  Time (c)
- After (-)\*: Time (f) < Time reference  $\leq$  Time (End)

By partitioning the study duration as periods of inhibitor status, analysis of time-dependent variables can be presented by inhibitor status.

*Inhibitor group*

An inhibitor group classifies a subject's inhibitor status overall during the study. Therefore, this classification is fixed for a subject, which differentiates itself from the classification by

inhibitor status for which a subject's inhibitor status may change from (-) to (+) over time according to his titre values.

The inhibitor positive group comprises of subjects who were confirmed (+) at any point during the study.

The inhibitor negative group comprises of subjects who were always (-) during the study.

For all subgroups defined in this section, in case of patients lower or equal than 3, the table will not be produced, data will only be provided in the listings.

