#### Arm 2 (PUPs)

##### Treatment success for major bleeding episodes

The number of bleeds and the number of treated bleeds will be presented. The percentage of bleeds treated successfully will be reported with a 95% CI. To estimate this percentage, the numerator will include the number of bleeding episodes treated with rVIII-SingleChain and rated as "excellent" or "good" (See Table 6 in Section 8.4.1 of the clinical protocol for details); and the denominator will include all treated bleeding episodes. Missing assessment will be counted as failures. With this approach, the following treated bleeds will be considered treatment failures in the primary analysis: those with ratings of "moderate", or "poor/none"; those treated with products other than rVIII-SingleChain regardless of the assessment; and those with missing investigator ratings. In order to account for within-subject correlation, generalized linear modeling using SAS' GENMOD procedure will be utilized. The model will contain only the intercept term. The binomial distribution with logit link function will be specified.

Two sensitivity analyses of the primary endpoint will be performed:

- In the first sensitivity analysis, missing investigator ratings will be excluded from the denominator.
- In the second sensitivity analysis, missing investigator ratings will be counted as treatment successes.

Results will be presented overall and by treatment modality.

Only bleeding episodes classified as major will be included in this analysis. Bleeding episodes reported by the subject in the eDiary will be excluded since major/minor classification is not collected.

Major and minor bleeds by inhibitor status will be summarized for PUPs.

CCI

Summary of rVIII-SingleChain treated bleeding events will be listed while inhibitor positive and per patient.

rVIII-SingleChain Non-Inhibitory Anti-Drug Antibodies, patient related risk factor, treatment related risk factor will be listed for PUPs.

Treatment related risk factor and patient related risk factor will be summarized by inhibitor group.

Bleeding events not treated with rVIII-SingleChain will be listed for PUPs.

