## 4.13 Algorithms/SAS Codes

- **Tables that need descriptive statistics – continuous variables:**

```
PROC UNIVARIATE DATA=dset NOPRINT;
  VAR var1 var2 var3 ...varn;
  BY byvar; (optional)
  OUTPUT OUT=outname
  N=n MEAN=mean MIN=min MAX=max MEDIAN=median STD=std Q1=q1 Q3=q3;
RUN;
```

- **Tables that need frequency counts:**

```
PROC FREQ DATA=dset NOPRINT;
  BY byvar; (optional)
  TABLES var1 *var2;
  OUTPUT OUT=outname;
RUN;
```

- **Tables that need 95% CIs within group for binomial proportions:**

```
PROC FREQ DATA=dset;
  BY byvar; (optional)
```

```
TABLES var1;  
EXACT BINOMIAL; RUN;
```

- **Tables that require generalized linear modelling, including 95% CIs:**

```
PROC GENMOD DATA= dset;  
  CLASS subject;  
  MODEL 'bleeding events / time on csf = < treatment>' /CL DIST=POISSON  
offset=logtime link=log;  
  LSMEANS < treatment> /diff=control exp cl;  
  WHERE wherever; (optional)  
RUN;
```

- **The geometric mean is the antilog of the arithmetic mean of the logs:**

```
DATA dset;  
  SET dset old;  
  LOGx = LOG(x);  
RUN;  
  
PROC UNIVARIATE DATA=dset NOPRINT;  
  VAR LOGx;  
  OUTPUT OUT=outname  
  MEAN=logmean;  
RUN;  
  
DATA outname;  
  SET outname;  
  geomean = EXP(logmean);  
RUN;
```

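### PUP bleeding-rate and bleed-success intervals: plain Poisson and intercept-only binomial models contain no term for differences between subjects, so their 95% CIs may be too narrow

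*SAP*

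**What the plan says.** **Bleeding rates.** Protocol 11.3.2.1 fits AsBR in GENMOD: "The Poisson distribution with log link function, and log_time offset will be specified". Protocol 11.3.2.2 repeats the analysis for ABR. SAP 4.6.1.1 (AsBR) commits to "The number of spontaneous bleeding episodes per year based on a Poisson model and associated 95% CI" and takes the prophylaxis/on-demand rate ratio and its interval from the same model. The template in SAP 4.13 has subject in the CLASS statement, then "MODEL 'bleeding events / time on csf = < treatment>' /CL DIST=POISSON" with an offset and log link. It has no REPEATED statement and no scale option.

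**Bleed success.** SAP 4.6.1.1 says of major bleeds: "In order to account for within-subject correlation, generalized linear modeling using SAS' GENMOD procedure will be utilized". What follows is an intercept-only model with a binomial distribution and logit link. Protocol 11.3.2.1 says the same, and Protocol 11.3.2.2 states that non-major "bleeding episodes will be analyzed as described in" that section. SAP 4.13 has no code for this model.

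**Context.** Subject-level AsBR is also summarised descriptively (Protocol 11.3.2.1, SAP 4.1). The percentage of subjects with zero bleeds is reported (SAP 4.6.1.1), and no p-values are planned (Protocol 11.3). The SAP reference list includes a longitudinal-GLM paper, which the visible methods text does not cite.

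**The concern.** A plain Poisson fit takes its standard error from the total number of bleeds alone, which is right only if every boy on a regimen has the same underlying rate. Listing subject in CLASS changes neither estimate nor standard error, because subject is not in MODEL and there is no REPEATED line. If boys differ, the printed interval claims more precision than the data hold, for a primary endpoint in about 24 subjects.

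The success model has a different fault: the text states an aim that the specified model cannot meet. An intercept-only binomial logit counts every bleed as independent, however many come from one boy.

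Neither model has a stated rule for no bleeds, or for all or no bleeds being rated successes. In those cases the usual log- or logit-scale interval does not exist.

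**Working it through.** The documents state no bleeding rate, spread, ICC or coverage, so there is no figure to reproduce. The results below are illustrations.

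**Inputs from the documents**
- Two-sided 95% intervals (SAP 4.1).
- 24 PUPs (Protocol 3.5; SAP 3.9, Sample Size Estimation). Another paragraph of SAP 3.9 says 50. More subjects would not cure the problem, because the ratio of true to printed standard error does not depend on n.
- Inhibitor-negative PUPs stay to 75 EDs (Protocol 3.3). At every second day, 3 or 2 doses a week (Protocol 3.2.1): 75/3.5 = 21.4, 75/3 = 25, 75/2 = 37.5 weeks. Times 7/365.25, T = 0.41, 0.48 or 0.72 years. On-demand follow-up would be longer.

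**Assumed:** 0.5, 1 or 3 spontaneous bleeds/year; gamma-distributed subject rates with shape 2, 1 or 0.5 (smaller means more spread); success probability 0.9; ICC 0, 0.1 or 0.3.

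**Step 1, bleeding rate.** Plain Poisson: SE(log rate) = 1/√(total bleeds). With gamma-distributed rates the true SE is larger by √(1 + rate×T/shape).
- 1/year, T = 0.41, shape 2: √(1 + 0.41/2) = 1.10
- 1/year, T = 0.72, shape 0.5: √(1 + 0.72/0.5) = 1.56
- 3/year, T = 0.72, shape 0.5: √(1 + 2.16/0.5) = 2.31

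Coverage is roughly 2Φ(1.96/factor) − 1, giving 93%, 79% and 60%. Simulation (20,000 per scenario, given at least one bleed) gives 95%, 82% and 61%. Over the three values of T and three shapes:

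| Rate per year | Plain Poisson, n=24 | Plain Poisson, n=12 |
|---|---|---|
| 0.5 | 89-97% | 92-96% |
| 1 | 82-95% | 84-96% |
| 3 | 61-90% | 62-89% |

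With no differences between boys the plain interval covers 95-97%. A subject-level sandwich SE times √(n/(n−1)) with t on n−1 covers 93-97% at n=24 and 92-98% at n=12. Without that correction, using z, it covers 91-96% and 88-96%, hence the t reference.

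**Step 2, rate ratio.** Rates 1 versus 3/year, 12/12 to 18/6 boys, nobody in both groups, follow-up 0.41 versus 0.72 or 0.72 versus 1.5 years: the plain interval covers 95-97% without heterogeneity and 64-94% with it.

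**Step 3, bleed success.** Naive SE(logit) = 1/√(N·p·(1−p)), N being all bleeds. With m bleeds per boy the true SE is larger by √(1 + (m−1)·ICC). At m=5 this is √1.4 = 1.18 (ICC 0.1) and √2.2 = 1.48 (ICC 0.3). Simulated naive coverage, 24 boys:

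| Bleeds per boy | ICC 0 | ICC 0.1 | ICC 0.3 |
|---|---|---|---|
| 1 | 97% | 97% | 97% |
| 2 | 95% | 95% | 93% |
| 5 | 95% | 91% | 82% |
| 10 | 96% | 87% | 72% |

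Robust intervals cover 94-97%. As a direct check, in one simulated data set (24 boys, 10 bleeds each) the intercept-only fit gave an SE of 0.195, identical to the independence formula; a GEE fit gave 0.301.

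**Step 4, boundary cases.** The chance of no bleeds is exp(−n·rate·T) without heterogeneity and (1 + rate·T/shape)^(−n·shape) with it. At n=12 and 0.5/year it runs from exp(−4.32) = 1% to 1.41^(−6) = 13%. The chance that all bleeds succeed at 0.9 (independent) is 0.9³ = 73%, 0.9⁵ = 59% and 0.9¹⁰ = 35%.

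**The case against.** The strongest reply is that this is a descriptive study. It has no p-values, sample-size calculation or margin, and nothing is decided on these intervals. Subject-level AsBR summaries and the zero-bleed percentage keep the spread between boys visible, and the documents never claim to handle over-dispersion in the rate model. All of that stands, and it limits the harm. It does not make a 95% interval on a primary endpoint correct if boys differ.

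The SAP 4.13 code is a schematic template, and the CLASS line and longitudinal-GLM reference suggest GEE was intended for bleed success. That also stands. A reader might infer that the success analysis is wrong; the documents support only that its mechanism is unstated. Major bleeds, the primary success endpoint, are life- or limb-threatening events (Protocol 8.3.2). At about one per boy the effect is nil.

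A reader might also blame repeated records from one boy, since "changes in treatment regimens (on-demand or prophylaxis) and dose modifications are allowed" (Protocol 3.2.5) and the SAP says "By partitioning the study duration as periods of inhibitor status, analysis of time-dependent variables can be presented by inhibitor status" (3.5.6). The documents do not support that. No passage describes a model pooling a boy's inhibitor-status periods as separate records. In simulation, with the same relative subject effect in both periods, regimen switching moves rate-ratio coverage back towards nominal: about 83-95% with 8 of 24 boys in both groups and 95-96% with all 24. The cause is variation between boys.

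Finally, a reader might extend the point to PTPs. The SAP records their report as completed in November 2019, and the model actually fitted cannot be seen, so nothing is claimed about those intervals.

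**Conclusion.** The point holds for PUPs and is minor to moderate. As written, the AsBR, ABR and rate-ratio intervals are valid only if boys on a regimen share one bleeding rate. The loss ranges from negligible (about 0.5 bleeds/year with modest spread) to serious (3/year with wide spread). The 61% figure is the extreme of an assumed grid, and nothing in the documents shows which case applies. For bleed success, the gap between stated aim and specified model matters mainly for the secondary non-major endpoint, and only if boys contribute several correlated bleeds each. The case for changing the rate model is that it is a cheap improvement. The case for changing the success model is that it would then do what the text says it does.

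**What to change.** For PUPs, in SAP 4.6.1.1 and 4.13:

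1. Poisson GENMOD: make the bleed count the response with the log-time offset, replacing the template's events-over-time expression. Add REPEATED SUBJECT=subject with empirical standard errors.
2. Binomial GENMOD for major and non-major success: add the same REPEATED statement.
3. For single-group intervals, multiply the SE by √(n/(n−1)) and use t on subjects minus 1, in a short post-processing step if needed. For the rate ratio, use the empirical SE and describe the interval as approximate.
4. If no bleeds occur, report an exact Poisson interval. If all or no bleeds succeed, use the exact binomial interval already coded in SAP 4.13. Note with each that it assumes independent events.

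**Cost:** a few SAP lines, a little programming and no new data. If boys do not differ, the median AsBR interval is 1-4% wider on the log scale at n=24 and 7-9% wider at n=12. If they do differ it is wider still (11-50% at n=24 and 1/year), as it should be. At about 12 boys per regimen the robust interval remains approximate.
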